### 8.1. Subject Inclusion Criteria

1. Male and female subjects age  $\geq$  18 years.
2. The subject must meet one of the following two criteria:
  - a. A positive influenza Rapid Antigen Test (RAT) and/or a FDA-approved PCR test and at least one clinical sign or symptom consistent with acute influenza infection as listed in 2b below.

**OR**

- b. Clinical signs and symptoms consistent with acute influenza infection consisting of an oral temperature  $\geq$  100°F (37.8°C) with at least one respiratory symptom of at least moderate severity (cough or rhinitis) and at least one constitutional symptom of at least moderate severity (myalgia [aches and pains], headache, feverishness, or fatigue). **Note: Enrollment at each site by clinical symptoms alone will be approved by the Sponsor at the beginning of each influenza season once influenza has been confirmed in the local community. The Sponsor may withdraw approval for symptomatic screening in any season based upon trends in influenza surveillance data. Prior to Sponsor approval or after approval is withdrawn, Criteria 2 must be met by a positive influenza RAT test and/or PCR. During the period of approval, clinical symptoms alone will be adequate to meet Criteria 2.**
3. Onset of symptoms no more than 48 hours before presentation for screening. However, due to historically delayed presentation for medical care in the adult population, approximately 20% of the elderly population may be enrolled with symptoms starting  $>$  48-hours but  $\leq$  72-hours prior to presentation for screening. Note: Time of onset of illness is defined as either (1) the time when the temperature (either oral or rectal) was first measured as elevated (at least one °C of elevated temperature), OR (2) the time when the subject experienced the presence of at least one respiratory symptom AND the presence of at least one constitutional symptom together.
4. Either age  $\geq$  65 years AND/ OR presence of one of the following risk factors:
  - a. Pregnancy, including women who are up to 2 weeks postpartum
  - b. Resident of a nursing home or long-term care facility
  - c. History of chronic lung disease including obstructive pulmonary disease (COPD), persistent asthma or cystic fibrosis
  - d. History of heart disease including myocardial infarction, angina requiring treatment, congestive heart failure requiring treatment, arrhythmia including atrial fibrillation and valvular dysfunction

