- Assessment of the presence and severity of each of 7 symptoms of influenza on a 4-point severity scale (0, absent; 1, mild; 2, moderate; 3, severe) at Screening, then twice daily through Day 13, and prior to the subject's clinic visit on Day 14 or until each symptom is 0 or 1 for 48 hours. Symptoms will be reviewed at each clinic visit.
- Temperature measurements (oral) will be taken with an electronic thermometer provided by the Sponsor, approximately every 12 hours until temperature normalizes for 48 hours (i.e. temperature without antipyretic is  $< 37.4^{\circ}\text{C} / 99.4^{\circ}\text{F}$  orally for 4 measurements). With the exception of the Screening/ Baseline measurement, all temperature measurements will be

obtained at least 4 hours after, or immediately before, administration of oral acetaminophen or other antipyretic medications, if taken.

- The type, date, and time of medications used for the symptomatic treatment of influenza-related symptoms.
- Assessment of the subject's ability to perform usual activities using a 0 to 10 visual analogue scale once daily through Day 14, where 0 = Unable to perform usual activities at all, and 10 = Able to perform all usual activities fully.

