3.3.4. Missing Data and Outliers

Every effort will be made to obtain required data at each scheduled evaluation from all subjects who have been enrolled. No attempt will be made retrospectively to obtain missing subject reported data (such as influenza symptom severity assessments and temperature) that has not been completed by the subject at the time of return of the subject diary to the investigative site. In situations where it is not possible to obtain all data, it may be necessary to impute missing data, as described in the following paragraph.

In assessing the effectiveness endpoint of time to alleviation of symptoms, for subjects who withdraw or who do not experience alleviation of symptoms, missing data will be censored using the date of subject's last non-missing assessment of influenza symptoms. For the subject diary data, the following data conventions will be utilized. Diary completion times will use a 24-hour clock. Missing diary completion times will be imputed as 11:59 for diary entries designated as morning and 23:59 for evening and daily reported values. Entries with values exceeding the 24-hour clock will be handled on a case-by-case basis and reviewed by a member of the clinical project team

prior to implementation. In general, values recorded between 24:01 – 24:59 will be interpreted as values past midnight and will be implemented as such. Values recorded as 60:00, 70:00, and 80:00 will be interpreted as 06:00, 07:00, and 08:00, respectively. Should additional data conventions be required, these will be documented in the derived variable specifications and in the final clinical study report. Other secondary effectiveness endpoints with time to event data will be censored using the date of subject's last non-missing assessment of the given endpoint.

Unless otherwise specified, no other missing data will be imputed.

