3.3.8. Definitions and Terminology

Age

Age will be defined as the age in years at time of signing of informed consent for all subjects.

Confirmed Influenza

A subject will be confirmed as having acute influenza infection if any specimen for assay of influenza A or B antigen by RT-PCR obtained during the study is positive.

Baseline Value

For purposes of analysis, the baseline value is defined as the last value obtained prior to initiation of study drug (eg, the Baseline Pre-Dose value). Should this value be obtained after the injection of study drug, then the most recent value obtained prior to initiation of study drug will be used for the baseline value.

Day 1

Day 1 is the day/time that study drug is initiated.

Study Day

Study Day is defined relative to Baseline (Day 1). Thus, the study day of an event is calculated as:
Study Day = event date – date of Day 1 +1.

Days on Study

Days on Study is the number of days from Day 1 to the date of study completion or early termination as recorded on the Day 14/End of Study/Early Withdrawal CRF.

Days of Subject Diary Completion

Days of Subject Diary Completion is defined as the number of days from Day 1 to the date of last Subject Diary completion. For the purposes of this analysis, the date of last Subject Diary completion is defined as the last date in which the Subject Diary had at least one complete assessment of symptoms recorded.

Alleviation of Symptoms

A subject has Alleviation of Symptoms if all of the assessed symptoms of influenza assessed on his/her subject diary are either absent or are present at no more than mild severity level and at this status for a 21.5 hour period (24 hours less 10%).

Composite Symptom Score

The Composite Symptom Score is defined as the sum of the seven symptoms of influenza (cough, sore throat, stuffy nose, muscle aches, headache, feverishness, fatigue/tired) assessed on a given time point within the subject diary.

Baseline Composite Symptom Score

The Baseline Composite Symptom Score is defined as the sum of the symptoms of influenza recorded by the subject in the diary corresponding to the assessment of a subject's symptoms prior to the initiation of study drug.

Resolution of Fever

A subject has Resolution of Fever if he/she has a temperature < 37.4°C/99.4°F oral and no antipyretic medications have been taken for at least 12 hours. Resolution of Fever is based on information obtained from the individual subject diaries.

Ability to Perform Usual Activities

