The ability to perform usual activities is defined as a subject rating of 10 (able to perform all usual activities fully) on the visual analog scale the subject uses to rate his or her current ability to perform usual activities compared with normal ability.

Time to Event

Time to a given event is defined as the number of hours (days) from initiation of earliest study treatment until the event occurs. The unit of measurement will vary based upon the endpoint and its respective schedule of assessment.

Time to Alleviation of Symptoms

Time to Alleviation of Symptoms is the number of hours from initiation of study drug to start of the 21.5 hour period (24 hours less 10%) where all symptoms of influenza are recorded as none or mild.

Change from Baseline

Change from baseline for a given endpoint is defined as the Study Day X value minus the Baseline Value.

Adverse Event (AE)

According to the protocol, an AE is any untoward medical occurrence in a clinical study subject. No causal relationship with the study drug or with the clinical study itself is implied. An AE may be an unfavorable and unintended sign, symptom, syndrome, or illness that develops or worsens during the clinical study. Clinically relevant abnormal results of diagnostic procedures including abnormal laboratory findings (eg, requiring unscheduled diagnostic procedures or treatment measures, or resulting in withdrawal from the study) are considered to be AEs.

AEs may be designated as “nonserious” or “serious” (see Protocol Section 11.1.1.1). Surgical procedures are not AEs but may constitute therapeutic measures for conditions that require surgery. The condition for which the surgery is required is an AE if it occurs or is detected during the study period. Planned surgical measures permitted by the clinical study protocol and the condition(s) leading to these measures are not AEs if the condition(s) was (were) known before the start of study treatment. In the latter case the condition should be reported as medical history.

Assessment of symptoms of influenza will be documented in a Subject Diary and analyzed as a measure of effectiveness of the study treatment. These symptoms will not be reported as AEs unless the symptom(s) worsen to the extent that the outcome fulfills the definition of a serious adverse event (SAE), which then must be recorded as such (see Protocol Section 11.1.1.2).

All AEs will be recorded on the ADVERSE EVENTS CRF.

Treatment-emergent Adverse Events (TEAEs)

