4.2. INTENT-TO-TREAT INFECTED POPULATION

The ITTI population will include all subjects who are enrolled, treated, and have influenza type A or B confirmed by PCR. The ITTI population will be used for analyses of effectiveness.

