5.1. SUBJECT DISPOSITION, DEMOGRAPHIC AND BASELINE CHARACTERISTICS

Subject disposition will be presented for all subjects. The number of subjects who completed the study and discontinued from the study will be provided. The reasons for early discontinuation also will be presented. Additionally, the number of days on study will be summarized.

A CONSORT diagram will be produced showing the number of subjects screened, number of screening failures, number of subjects by age group, number in each of the study populations, and number who complete the study.

Demographic data and baseline characteristics including age, gender, race, ethnicity, Baseline Composite Symptom Score, baseline viral titer status, the number subjects who had hypothermia ($< 35^{\circ}\text{C}/95^{\circ}\text{F}$), normal temperature (35 to $< 37.4^{\circ}\text{C} / 95$ to $< 99.4^{\circ}\text{F}$), or fever ($\geq 37.4^{\circ}\text{C}/99.4^{\circ}\text{F}$) at baseline, height, weight, and body mass index (BMI) will be summarized using descriptive statistics for the ITT, ITTI, safety, and exposure-response populations.

Enrollment by site, eligibility, treatment status, and screening RAT and PCR test results will be summarized by age group and overall.

This information will be reviewed for baseline differences, but no statistical testing will be performed.

Subject diary completion will be summarized including the days of diary completion.

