5.2.2. Effectiveness Analyses

A subject's oral temperature taken by subjects and recorded in the diary by subjects/caregivers will be summarized by age group and overall by study visit. A subject has Resolution of Fever if he/she has an oral temperature $< 37.4^{\circ}\text{C}/99.4^{\circ}\text{F}$ oral and no antipyretic medications have been taken for at least 12 hours. The time to resolution of fever will be estimated for each age group and overall using the Kaplan-Meier method with temperature and symptom relief medication information obtained from the subject diary data. Subjects who do not have resolution of fever will be censored at the time of their last non-missing post-baseline temperature assessment.

Alleviation of symptoms will be determined by assessment of symptoms as reported on each Subject Diary. The time to alleviation of symptoms, defined as the time from initiation of study drug until the start of the 21.5 hour period (24 hours less 10%) where all symptoms of influenza are recorded as none or mild, will be estimated overall and for each age group using the Kaplan-Meier method. Subjects who do not experience alleviation of symptoms will be censored at the date of their last non-missing post-baseline assessment.

Change from baseline in \log_{10} TCID₅₀/mL through Day 3, Day 7, and Day 14 will be presented by age group and overall for subjects with positive viral titers at baseline (\log_{10} TCID₅₀/mL > 0.5). A box plot and a histogram of the TCID₅₀/mL values will be presented by visit and age group. In addition, the median change from baseline in TCID₅₀/mL will be presented by visit and age group.

The number and percent of subjects with positive viral titers at baseline (\log_{10} TCID₅₀/mL > 0.5) that shed virus at each visit will be presented by age group and overall.

The RT-PCR results at each visit will be presented by age group and overall for subjects with positive RT-PCR results at baseline.

Change from baseline to last positive value of influenza virus susceptibility to neuraminidase inhibitors will be assessed using virology laboratory tests. Virology laboratory tests will include phenotypic characterizations of influenza virus recovered (hemagglutinin and neuraminidase) and viral susceptibility to zanamivir, oseltamivir, and peramivir, as well as genotyping of virus isolates. These analyses will be presented overall and by age group and viral subtype.

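### Time to resolution of fever is run on all infected subjects, so those with no fever at baseline count as early resolutions

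*SAP*

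**What the plan says.** **Entry.** Protocol 8.1, criterion 2a, requires "A positive influenza Rapid Antigen Test (RAT) and/or a FDA-approved PCR test and at least one clinical sign or symptom" consistent with influenza. The temperature threshold of 37.8 °C appears only in the alternative, 2b. The extra screening text in Protocol 10.1.1 asks for a respiratory and a constitutional symptom of at least moderate severity, but not for a measured temperature.

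**Population.** SAP 4.2 defines ITTI as enrolled, treated and PCR-confirmed, and adds: "The ITTI population will be used for analyses of effectiveness". It sets no temperature condition. The fever table and figures in SAP 9 (14.2.1.2 to 14.2.1.5) are titled for ITTI without a qualifier.

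**Baseline.** SAP 5.1 tabulates "the number subjects who had hypothermia", normal temperature, or fever (37.4 °C or above), and does so for ITTI among other populations.

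**Event and clock.** SAP 3.3.8 defines resolution as an oral diary temperature below 37.4 °C when "no antipyretic medications have been taken for at least 12 hours". On the clock it says: "Time to a given event is defined as the number of hours (days) from initiation of earliest study treatment until the event occurs". SAP 3.3.4 adds: "Diary completion times will use a 24-hour clock". Protocol 10.1 has temperature taken "approximately every 12 hours until temperature normalizes for 48 hours".

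**Analysis.** SAP 5.2.2 says: "The time to resolution of fever will be estimated for each age group and overall using the Kaplan-Meier method". Its only special rule censors subjects who do not resolve. In the same section, the titer, shedding and RT-PCR summaries are limited to subjects positive at baseline.

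**The concern.** A time-to-resolution curve should describe people who have something to resolve. Nothing in the definition requires a febrile reading first, and no rule excludes subjects who start without fever or assigns them a time. A programmer following the text would give such a subject an event at the first diary reading that meets the temperature and antipyretic conditions.

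The result would be a shorter reported median. It could also produce differences between age groups or viral subtypes that reflect only different afebrile shares, even if febrile subjects recovered identically. The trial has no control arm in which the same distortion would appear and offset it. Protocol 7.1.2 lists the endpoint as secondary, and Protocol 9.9.1 describes fever resolution as important. Medians with 95% confidence intervals, Kaplan-Meier plots and box plots are all planned.

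**Working it through.** **Text check.** Four conditions must all hold for the problem to exist:

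1. Afebrile subjects can enter. Criterion 2a allows it, and Protocol 10.1.1 does not prevent it.
2. They stay in the analysis set. SAP 4.2 and the output titles have no temperature condition.
3. They can meet the event definition without prior fever. SAP 3.3.8 and 5.2.2, and Protocol 13.8.2, require none.
4. No rule removes them. Only subjects who never resolve are addressed, by censoring.

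All four hold. The plan gives no figure to reproduce, so the rest is an illustration.

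**Inputs from the documents.** Time runs from each subject's own dose, and diary readings are roughly 12 hours apart with recorded clock times, so subjects share no common reading grid.

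**Assumed inputs.**
- Febrile resolution time T is exponential, or lognormal with sigma 0.8. Its median is 48 h, varied from 36 to 72 h.
- The first reading U is uniform over 0–12 h after dosing. Later readings fall at U + 12k.
- f is the share afebrile at baseline.
- a is the share of afebrile subjects whom antipyretic use delays to the febrile distribution.
- g = f(1 − a) is the share counted as resolved at U.

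**Formula.** Let G(t) be the average over U of F(last reading at or before t), where F is the distribution function of T. The observed median t\* solves

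g·min(t/12, 1) + (1 − g)·G(t) = 0.5.

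Once t\* exceeds 12 h, this becomes G(t\*) = (0.5 − g)/(1 − g). At g = 0.10 that is 0.40/0.90 = 0.444. At g = 0.20 it is 0.30/0.80 = 0.375. The median of a mixture is thus a lower percentile of the febrile curve, whatever that curve's shape.

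**Results, febrile median 48 h, a = 0:**

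| Afebrile share | Exponential (h) | Lognormal (h) |
|---|---|---|
| 0% | 54.1 | 54.1 |
| 5% | 50.5 | 51.7 |
| 10% | 46.8 | 49.0 |
| 20% | 38.6 | 43.3 |
| 30% | 29.4 | 36.6 |
| 35% | 24.3 | 32.6 |

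The value with none afebrile exceeds 48 h because resolution is seen only at the next reading, about 6 h later on average. A simulation with 2,000,000 subjects at a = 0 agreed within 0.1 h.

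**Apparent group difference.** With identical febrile recovery but 10% and 30% afebrile, the medians are 46.8 and 29.4 h (difference 17.4 h) for the exponential, and 49.0 and 36.6 h (difference 12.5 h before rounding) for the lognormal.

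**Antipyretic use in afebrile subjects, f = 10/20/35%:**

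| a | Exponential (h) | Lognormal (h) |
|---|---|---|
| 0.3 | 49.1 / 43.6 / 34.6 | 50.6 / 46.8 / 40.4 |
| 0.6 | 51.3 / 48.3 / 43.6 | 52.2 / 50.1 / 46.8 |

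**Other febrile medians, a = 0, f = 0/10/20%:**

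| Febrile median | Exponential (h) | Lognormal (h) |
|---|---|---|
| 36 h | 42.1 / 36.6 / 30.5 | 42.2 / 38.3 / 34.0 |
| 72 h | 78.1 / 67.1 / 54.9 | 78.1 / 70.5 / 61.9 |

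Across 36–72 h the relative fall is 9–14% at 10% afebrile and 19–30% at 20%.

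**Early part of the curve, g = 0.20.** The share resolved by 12 h rises from 0.082 to 0.20 + 0.80 × 0.082 ≈ 0.27 (exponential), or from 0.010 to 0.20 + 0.80 × 0.010 ≈ 0.21 (lognormal).

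**The case against.** **The 12-hour look-back.** Medication information comes from the diary, and diary training follows dosing (Protocol 10.1.2.2). On a strict diary-only reading, no one can be shown free of antipyretics for 12 hours until a reading 12–24 h after dosing. The share resolved by 12 h would then be zero in every scenario. This stands as a caveat on that one figure, because the SAP does not say whether prior-medication records may fill the gap. Every median shown above exceeds 24 h and is unchanged, because all the affected afebrile subjects have resolved by then under either reading.

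**Assumed size and sampling noise.** All illustration inputs are assumptions, and heavy antipyretic use would leave only a small shift. With 80 subjects, simulation puts the 95% sampling range of the median at about 41–71 h (exponential) or 45–66 h (lognormal), wider than the shift at 10% afebrile. Both points are fair, but noise does not remove a bias whose direction is fixed.

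**Comparators.** The virology restriction is partly a measurement necessity, and the other time-to-event endpoints carry no baseline restriction either. That weakens the contrast with virology without supplying a rule for fever. Protocol 10.1.1 also asks for moderate symptoms at entry, which gives the symptom endpoint something to alleviate. No matching requirement exists for temperature.

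**The febrile subset has its own selection.** Protocol 10.2.1 records baseline temperature whether or not an antipyretic was recently taken, so some masked fevers would be left out. This is true, and it is why a screening fever should also qualify and the all-ITTI analysis should be kept.

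**Low stakes.** The endpoint is descriptive, and SAP 5.1 already shows the afebrile share. That share tells the reader a problem may exist but does not correct the curve or the median.

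**Conclusion.** The concern holds. Followed as written, the plan counts ITTI subjects who are afebrile at baseline as fever resolutions, and the bias runs toward faster recovery. That conclusion rests on the text alone. The size cannot be derived from the documents. Under the stated assumptions with no antipyretic use in afebrile subjects, a 10% afebrile share lowers the median by about 5–7 h from 54 h, and 20% lowers it by about 11–15 h. If antipyretics delay 60% of afebrile subjects, those falls shrink to about 2–3 h and 4–6 h. There is no afebrile share below which the median does not move. No hypothesis is tested, so the harm is a misleading descriptive estimate and possibly spurious age or subtype contrasts. It should be fixed, but it does not threaten the trial's primary safety objective.

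**What to change.** In SAP 5.2.2, define the main fever analysis set as ITTI subjects with a temperature of 37.4 °C or above, the SAP's own fever category, at screening or pre-dose baseline. Apply it to Tables 14.2.1.2 and 14.2.1.2.X and Figures 14.2.1.3 to 14.2.1.5, with titles to match. Report the number excluded by age group. Keep the all-ITTI analysis as a sensitivity analysis. Record the change in SAP 6, because Protocol 13.5 assigns effectiveness analyses to ITTI. Add a footnote that the excluded count can be lower than the afebrile count in Table 14.1.4.2, since a screening fever also qualifies.

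The cost is some SAP wording and one flag built from temperatures already collected before dosing. The fever analysis will have fewer subjects and longer, less favourable medians. Subjects whose fever was masked by an antipyretic at both readings drop out of the restricted set but remain in the all-ITTI analysis.

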#### **9.9. Concomitant Medications**

With the exception of medications used for the symptomatic treatment of influenza-related symptoms, administration of any dose of a concomitant medication during the study period must be recorded by the study staff within the subject's study source documents (e.g., chart). This includes prescription medications as well as over-the-counter medications.

Medications, such as antipyretics and analgesics, used for the symptomatic treatment of influenza-related symptoms will be recorded separately. Subjects will record the type, date, and time of symptomatic medications in the subject diary supplied by BioCryst including the date and time of administration. Study staff will provide diary completion instructions to subjects during their first study visit.

Use of concomitant medications will be assessed and recorded at Screening, and daily throughout the duration of the study through the study completion visit at Day 14 or later.

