##### **10.1.2.2. Day 1/Post-dose**

The following procedures/evaluations will be performed post-dose on Day 1:

- Collect up to 3 plasma samples, where possible, during the following time periods, beginning from the end of dosing until release from the site. For each plasma sample the calendar date and 24-hour clock time of sample collection will be recorded:
  - One time point immediately following completion of the infusion
  - One time point from 30 minutes to 1 hour post-infusion
  - One time point from 1 hour to 3 hours post-infusion
- Train the subject/caregiver on the recording of the following in the subject diary:
  - Subject's body temperature, obtained at approximately 12-hour intervals each day until the temperature normalizes for 48 hours (and 4 hours from last antipyretic medication administration or immediately prior to administration).

- Instruct the subject to assess his/her time lost from work, if applicable, and the recording of the subject's ability to perform usual daily activities using a 0 to 10 visual analogue scale.
- Assessment of signs and symptoms of influenza twice daily beginning on Day 1 (see Section [10.2.2](#)).
- Review and record concomitant medications
- Obtain and record body temperature
- Review and record AEs

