#### **10.2.1. Body Temperature**

The Investigator will record oral body temperature at Screening. The baseline temperature will be recorded at the Day 1 visit prior to dosing, regardless of whether the subject had recently taken an antipyretic. Thereafter, the subject or caregiver will record oral body temperatures approximately every 12 hours through Day 14 in the subject diary. Subjects or caregivers will measure their oral temperature with an electronic thermometer (provided by the Sponsor for the study). With the exception of the

baseline measurement, subjects will be instructed to take all temperature measurements at least 4 hours after, or immediately before, administration of oral acetaminophen or other antipyretic medications. The times of each temperature determination will be recorded in the Subject Diary.

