5.3.2. Concomitant Medications

Prior and concomitant medications, as well as symptom relief medications recorded on the subject diary, will be coded using the World Health Organization (WHO) drug dictionary (Version: March, 2015). All concomitant medications, antipyretic concomitant medications, and concomitant medications used to treat influenza symptoms will be summarized by frequency of drug classification and generic drug name. Prior and concomitant medications will be presented in a data listing. Symptom relief medications will be presented in a data listing.

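### The 12-hour antipyretic-free check for fever resolution uses the subject diary alone, so readings within about 12 hours of the diary's start can count as resolved despite a recent antipyretic

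*SAP*

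**What the plan says.** **Event.** SAP 3.3.8 and 5.2.2 require an oral temperature below 37.4 °C (99.4 °F) and that "no antipyretic medications have been taken for at least 12 hours". No sustained period below the threshold is required.

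**Data source.** SAP 5.2.2 estimates the Kaplan-Meier curve from "temperature and symptom relief medication information obtained from the subject diary data". SAP 3.3.8 agrees: "Resolution of Fever is based on information obtained from the individual subject diaries". The protocol's definition (13.8.2) has the same two conditions but names no data source.

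**Clock.** SAP 3.3.8: "Time to a given event is defined as the number of hours (days) from initiation of earliest study treatment until the event occurs".

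**Start of the diary.** Protocol 10.1.2.2, which lists the Day 1 procedures after dosing, includes: "Train the subject/caregiver on the recording of the following in the subject diary".

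**Antipyretics before dosing.** Protocol 10.2.1 has the baseline temperature taken before dosing, "regardless of whether the subject had recently taken an antipyretic". SAP 3.3.8 classes drugs taken before study drug as prior medications.

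**Where antipyretics are recorded.** Protocol 9.9 gives study staff the job of recording other drugs in the source documents: "With the exception of medications used for the symptomatic treatment of influenza-related symptoms, administration of any dose of a concomitant medication". Protocol 9.9.1 has the subject or caregiver enter names and times of antipyretics and analgesics given during enrolment in the diary, with no limit by reason for use. SAP 5.3.2 adds: "All concomitant medications, antipyretic concomitant medications, and concomitant medications used to treat influenza symptoms will be summarized". That summary is not linked to the fever endpoint.

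**The concern.** The rule looks back 12 hours, but the only record it consults starts on Day 1 around or after dosing. For early readings, part of the look-back falls in time the diary does not cover. The SAP gives no rule for a reading with less than 12 hours of diary history. On the natural reading, an empty diary counts as no antipyretic.

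The error runs one way: a missed antipyretic can turn a non-qualifying reading into a qualifying one, never the reverse. Because one reading is enough, an early false event fixes that subject's time. Protocol 9.9.1 calls fever resolution an important endpoint and wants antipyretic use carefully documented. In a single-arm study the Kaplan-Meier median is itself the result, and no control group shares the bias.

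**Working it through.** The plan gives no figure to reproduce: there is no sample size calculation, expected fever duration or rate of antipyretic use. The check compares the look-back with the coverage of the diary.

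**1. Look-back hours that the diary does not cover.** Inputs are the 12-hour look-back (SAP 5.2.2), readings about every 12 hours (Protocol 10.2.1) and time zero at the start of study drug (SAP 3.3.8). The start of the diary, *s* hours after dosing, is an assumption, because the documents give only its place in the procedures. For a reading *t* hours after dosing, with *t* at or after *s*:

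uncovered hours = 12 − (*t* − *s*), and zero once *t* − *s* reaches 12.

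| Diary start *s* | *t* = 3 h | *t* = 6 h | *t* = 9 h | *t* = 12 h | *t* = 15 h |
|---|---|---|---|---|---|
| 0 h | 9 | 6 | 3 | 0 | 0 |
| 1 h | 10 | 7 | 4 | 1 | 0 |
| 3 h | 12 | 9 | 6 | 3 | 0 |

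The gap closes 12 hours after the diary starts. With 12-hourly readings it touches roughly one reading per subject.

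**2. Does the protocol's spacing instruction close it?** Protocol 9.9.1 asks for temperatures at least 4 hours after an antipyretic, whenever possible. A dose taken 4 to 12 hours before the reading meets that instruction and fails the endpoint rule. If it was taken before the diary began, the derivation does not see it.

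**3. Hypothetical subject.** Acetaminophen at 13:00, infusion and diary start at 14:00, first diary reading 37.1 °C at 20:00. The look-back runs from 08:00 to 20:00, and the diary covers 14:00 to 20:00. The event is recorded at 20:00 − 14:00 = 6 h, although the reading is 20:00 − 13:00 = 7 h after a dose. With the earlier dose visible, the next reading, at 08:00 the following day (18 h after study drug and 19 h after the antipyretic), is the first that could qualify.

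**4. Sensitivity of the median (illustration only).** Suppose a share *f* of subjects gets a false event at the first reading, unrelated to their true time, and true times are exponential with median *M*. Solving (1 − *f*) × 2^(−*t*/*M*) = 0.5 gives *t* = *M* × (1 + log2(1 − *f*)), valid while the result exceeds the first reading time.

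| Assumed *M* | *f* = 5% | *f* = 10% | *f* = 20% |
|---|---|---|---|
| 24 h | 22.2 h | 20.4 h | 16.3 h |
| 36 h | 33.3 h | 30.5 h | 24.4 h |
| 48 h | 44.4 h | 40.7 h | 32.5 h |

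Both *f* and *M* are assumed. *f* is a joint proportion: an antipyretic inside the window but outside the diary, a reading below 37.4 °C, no diary-logged dose in the window, and fever not truly resolved. The documents support no value for it.

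**5. Antipyretics recorded only as concomitant medication.** Protocol 9.9 keeps drugs taken for reasons other than influenza symptoms in staff records, while 9.9.1 sends antipyretics and analgesics to the diary. A site following 9.9 could record a regular analgesic outside the diary at any time in follow-up, so this gap is not confined to the first 12 hours. A site following 9.9.1 would not create it.

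**The case against.** - **The diary may hold pre-dose information.** SAP 3.3.8 takes the baseline symptom score from a pre-dose diary entry and says that subjects record the medications they are currently taking. Neither provides a timed 12-hour antipyretic history before dosing. Protocol 9.9.1 covers antipyretics given during enrolment. This objection does not remove the gap.
- **Protocol 9.9.1 is the specific rule and governs antipyretics.** This largely stands. A reader might infer that antipyretics taken for other conditions generally escape the endpoint. The documents do not support that: 9.9.1 is not limited by reason for use, and nothing says that the antipyretic table in SAP 5.3.2 excludes diary entries. What remains is the conflict with 9.9.
- **Pre-dose use is permitted, not predicted.** This stands. A reader might infer that the typical subject arrives having taken an antipyretic, but Protocol 10.2.1 says only that the baseline reading is taken either way.
- **A reading 7 hours after a dose meets the protocol's own 4-hour standard.** Also true. Such a reading breaks the 12-hour rule, but the documents do not show that the drug was hiding a fever.
- **The drugs are not lost.** Prior and concomitant medications are listed in Listing 16.2.4.5. They are missing only from the endpoint derivation.

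**Conclusion.** The concern holds for readings within about 12 hours of the diary's start. They can be scored as resolved although an antipyretic was taken within 12 hours, and the bias is towards earlier resolution. This rests on the natural reading that an incomplete history counts as antipyretic-free, which the SAP neither states nor excludes. A second, smaller gap follows from the conflict between Protocol 9.9 and 9.9.1.

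The size cannot be computed from the documents. A reader might take the table of medians as an estimate of bias, but it only shows how the median would respond to assumed shares and durations. The endpoint is secondary and descriptive, with no hypothesis test, so no error rate or sample size is affected. That a single reading suffices for the event is a separate matter, which the change below does not address.

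**What to change.** In SAP 3.3.8 and 5.2.2:

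1. Apply the 12-hour check to diary entries plus timed antipyretics in the prior and concomitant medication data.
2. Let a reading less than 12 hours after the diary's start qualify only if those combined data show no antipyretic in the preceding 12 hours.
3. If a pre-dose antipyretic on Day 1 has no clock time, treat only readings in the first 12 hours after the start of study drug as non-qualifying. The dose cannot be later than time zero, so later readings are clear of it.
4. Do not make whole calendar days non-qualifying for untimed chronic medications. A subject on an untimed daily analgesic could then never resolve, and a short bias would be replaced by a long one. Show untimed chronic analgesic use as a sensitivity analysis.
5. State that, for this derivation, the low-dose aspirin permitted by Protocol 9.9.1 does not count as an antipyretic.

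Protocol 9.9 and 9.9.1 should also be reconciled on where antipyretics are recorded.

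The cost is SAP wording and one dataset merge, and the median may become slightly longer. SAP 5.3.2 already codes both sources. The documents require clock times for diary medications but state no such requirement for the prior and concomitant records, so check how many of those entries carry a time.
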